6.3 Analysis of Secondary and exploratory outcomes

As with the primary outcomes, analysis for secondary outcomes will be undertaken using GEE with robust errors for both continuous and binary outcomes. The secondary and exploratory outcomes are explained in table 1.

1) Eligibility rate – secondary outcome

Eligibility of an adolescent to receive counselling is defined as per the eligibility criteria outlined in table 1. The 'eligibility' of a referred adolescent in period 'l' can be described as

$$Y_{ijkl} = \begin{cases} 1 & if \ student_{ijk} \ identified \ as \ 'eligible' \ in \ period \ l \\ 0 & else \end{cases}$$

where Y_{ijkl} is as before (in section 6.2). The analysis of effect of the school sensitization (control) and classroom sensitization (intervention) on the referral of eligible adolescents will be modelled on the method described in section 6.2 for primary outcome using GEE and the specification of family: binomial, link function: logit, correlation structure: independent and with robust standard errors.

2) Self-referral rate – secondary outcome

The referral source will be described as a binary variable, coded as 1 for referrals through self (including those that were referred through direct walk-in or through the drop-box), and 0 for all other sources combined (including teachers, parents, friends, siblings).

$$Y_{ijkl} = \begin{cases} 1 & if \ student_{ijk} \ is \ referred \ by \ self \ in \ period \ l \\ 0 & else \end{cases}$$

Analysis will be undertaken to describe the population averaged odds of self-referral across the two conditions, using GEE method with robust standard errors as described in section 6.2 for analysis of the primary outcome and include the specification of family: Binomial, link function: logit, correlation structure: independent and with robust standard errors.

3) Severity of mental health symptoms – exploratory outcome

For every student referred, the severity of the mental health symptoms will be assessed using the Total Difficulties score measured on SDQ. We will use SDQ Total Difficulties score as a continuous measure. We will use GEE with robust standard errors for estimating the effects of the intervention on the reported severity of mental health symptoms. The regression equation will be modelled to include the effects of immediate and continued effects of school and classroom sensitization activities

as outlined for analysis of primary outcome in section 6.2. The GEE model will include specifications of family: Gaussian, link function: identity, correlation structure: independent, standard errors type: robust.

4) Severity of mental health symptom sub-types - exploratory outcome

Along the lines of the analysis described for the severity of mental health symptoms above, mean scores (provided the student was referred and then assessed on SDQ), for each of the sub-scales for internalising symptoms and externalising symptoms will be calculated as described in table 1. Using these scores as continuous variable, we will analyse for the severity of internalising and externalising symptoms separately, across the control and the intervention conditions.

We will use GEE with robust standard errors for estimating the effects of the intervention on the reported severity of mental health symptoms with model specifications as described for analysis of secondary outcome – severity of mental health symptoms. The GEE model will include specifications of family: Gaussian, link function: identity, correlation structure: independent, standard errors type: robust.

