The primary hypothesis is that the classroom-level sensitization intervention will be associated with a higher referral rate into the host trial, compared with referrals arising from school-level sensitization activities in isolation.

The secondary hypotheses are:

- Compared with the control condition, the intervention condition will be associated with a greater proportion of referred students who meet eligibility criteria for inclusion in the host trial.
- Compared with the control condition, the intervention condition will be associated with a greater proportion of students who self-refer.
- Compared with the control condition, the intervention condition will be associated with adolescents reporting a greater severity of total symptoms experienced and a greater severity of internalising and externalising symptom types.

Outcome	Outcome Explanation						
PRIMARY OUTC							
Referral rate into the host trial	The referral rate will be calculated as the number of referred students from a given condition divided by the total number of students in corresponding classes. This will be calculated from researchers' referral logs. Referrals will be recorded continuously and reported for each 4 weeks' time period, for the total study duration of 12 weeks. It will be entered as a binomial variable at the student level indicating if student was referred during the trial	Referral logs					
SECONDARY OU	TCOMES						
Eligibility rate	Eligibility rate is defined as the proportion of referred participants meeting eligibility criteria for the host trial, as a function of the number of referred adolescents in a given condition. Host trial eligibility criteria are as follows: (i) Total Difficulties score on the adolescent-reported Strengths and Difficulties Questionnaire (SDQ) >/= 19 for boys & >/= 20 for girls (2); (ii) SDQ Impact Supplement score of >/=2; and (iii) chronicity of mental health problems for >/= 1 month. Referred students will complete the SDQ as part of the host trial's screening assessment, within 7 working days of the referral date. Eligibility rate will be calculated for each of the 4-week time periods and reported for the entire study duration of 12 weeks. It will be entered as a binomial variable at the student level indicating if referred student is "eligible" to receive counselling.	Adolescent reported SDQ					

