6.2 Analysis of primary outcome

In this section, we describe the statistical analysis for the primary outcome. The intervention delivery in the intervention condition at class level (cluster). As we know the size of classes and have the data for all the referred students in each of the time periods, we are able to construct the data at the individual level:

$$Y_{ijk} = \begin{cases} 1 & if \ student_{ijk} \ referred \\ 0 & else \end{cases}$$

where i = 0 or 1 (0 = control condition, 1 = intervention condition), $j = 1, ..., m_i$ (number of classes in each condition), $k = 1, ..., n_{ij}$ the number of students in class j in condition i. We therefore have observations nested within students and students nested within classes. The primary analysis takes data of all three time periods into account. So, we have

$$Y_{ijkl} = \begin{cases} 1 & if \ student_{ijk} \ referred \ in \ period \ l \\ 0 & else \end{cases}$$

where l = 1, 2 or 3 to indicate the period.

Figure 3: Trial schematic indicating the effects that can be measured (adapted from figure 1)

		Step 1	Step 2
Sequence 1 (1-35 classes)	Control condition (immediate control effect)	Intervention condition (immediate intervention effect)	Intervention condition (continued intervention effect)
Sequence 2 (36-70 classes)	Control condition (immediate control effect)	Control condition (continued control effect)	Intervention condition (immediate intervention effect)
Time	1 st time period (4 weeks)	2 nd time period (4 weeks)	3 rd time period (4 weeks)

We can describe the following effects of the intervention (figure 3):

- The classes in sequence 1 and sequence 2 underwent the immediate effect of the school level sensitization intervention (control condition) at the first period.
- The classes in sequence 1 and sequence 2 underwent immediate effects of receiving classroom sensitization intervention (intervention condition) in the second and third time periods respectively the main parameter of interest.
- The classes in sequence 2 underwent continued effects of receiving school level sensitization intervention (control condition) in second time period.
- The classes in the sequence 1 underwent continued effects of receiving the classroom sensitization intervention (intervention condition) in the third time period.

These effects can be described in the following equation

$$logit\left(P(Y_{ijkl})\right) = \theta_0 + \theta_1 X_{li} + \theta_2 T_{2l} + \theta_3 T_{3l}$$

Where:

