We have data with three records for each student, for time period 1, 2 and 3, with students nested in classes. The calculation of the parameters will need to account for this clustering of data at the class level. Analysis will be undertaken using Generalized Estimating Equations (GEE) with robust standard errors that are measured using the sandwich estimator method. GEE is a general statistical approach to fit a marginal model for longitudinal/ clustered data analysis. GEE was introduced by K. Liang and S. Zeger(13) to analyse longitudinal data without resorting to fully specified random effect models and can be applied to both continuous and categorical outcomes. It is a recommended method for analysis of the stepped wedge cluster randomised controlled trials(14), and provides population averaged effects of exposure to the interventions across the control and intervention conditions. GEE provides both parameter estimates and standard errors that are corrected for clustering of data and are consistent despite misspecifications in the correlation structure. For these reasons, GEE is a suitable method for analysis of primary outcome in this trial.

The analysis will be carried out using "xtgee" command using Stata 15.1. The panel structure of data and clustering of data at class level will be specified through stata command "xtset". The following will be specified in the GEE model:

- Family of distribution of the response variable: Binomial as the outcome variable is binary.
- Link function: Logit link function.
- The within-group correlation structure will be specified as independent.
- Standard error type: robust.

Having a variable for indicating the class in which student observations are nested (class_id), outcome variable indicating the referral status of the adolescent (referred), time indicator (t2) for period 2 for classes that continue to experience school based sensitization activities, indicators for the immediate and continued effects of classroom sensitization activities (effect_lag0 and effect_lag1), the parameters will be estimated using the stata command as illustrated below:

"xtset class_id"

"xtgee referred t2 effect_lag0 effect_lag1, family(binomial) link(logit) corr(independent) vce(robust)"

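### SAP 6.3, item 1, leaves room for an all-student model of 'referred and eligible', although the eligibility rate is defined among referred students

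*SAP*

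**What the plan says.** **Text that limits eligibility to referred students.** Table 1 gives the eligibility rate "as a function of the number of referred adolescents in a given condition" and enters it as a variable describing a referred student. The secondary objective and hypothesis in section 3 use the same denominator. Section 4.2 lists eligibility for referred students and says that SDQ data come from them alone. Section 6.3 opens by pointing back to those definitions: "The secondary and exploratory outcomes are explained in table 1". The lead-in to the eligibility equation speaks of the eligibility "of a referred adolescent in period" l.

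**Text that points to all students.** The equation assigns 1 to a student identified as eligible in the period and 0 otherwise. The item then says that Y "is as before (in section 6.2". In 6.2 the index k runs up to "the number of students in class j in condition i". The zeros for non-referred students are built there from class sizes ("As we know the size of classes and have the data for all the referred students in each of the time periods"), and the data set is described thus: "We have data with three records for each student, for time period 1, 2 and 3, with students nested in classes". Last, the target sentence describes the effect of the two conditions "on the referral of eligible adolescents will be modelled on the method described in section 6.2 for primary outcome using GEE".

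Item 1 has no separate statement of which records enter the model, and no Stata command of its own.

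**The concern.** The two sets of passages describe different quantities. Table 1 asks what share of referrals is eligible. The target sentence in 6.3 names the number of eligible referrals; with the 6.2 data set underneath, that becomes a yield per enrolled student. The yield is the referral rate multiplied by the eligible share, so it rises with the primary outcome even when the share is unchanged.

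The secondary hypothesis is that the classroom session increases the eligible share. Under the all-student model, a repeat of the primary result could be read as support for that separate hypothesis, even if the share had fallen. Two analysts could follow item 1 in good faith and fit different models.

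**Working it through.** The SAP gives no figure for the eligibility outcome, so there is none to reproduce. The check compares what the two readings would estimate.

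**Inputs.** From section 3.6: referral rates of 5% (control) and 15% (intervention), 70 classes, 50 students per class, ICC 0.124. Assumed, because the SAP gives none: the eligible share s among referrals. It is also assumed that the 5% applies to period 1 and the 15% to the first intervention period.

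**Which contrast.** The 6.2 model has three cell indicators and an independence working correlation. The main parameter is therefore the crude log odds ratio of first-intervention-period records against period-1 records, and crude odds ratios can be used directly.

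**Formulas.**
- Referred only: OR = [s1/(1−s1)] / [s0/(1−s0)]
- All students: OR = [0.15·s1/(1−0.15·s1)] / [0.05·s0/(1−0.05·s0)]

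| Share, control → intervention | Referred only | All students |
|---|---|---|
| equal, near 0 | 1.00 | 3.00 |
| 30% → 30% | 1.00 | 3.09 |
| 50% → 50% | 1.00 | 3.16 |
| 70% → 70% | 1.00 | 3.23 |
| equal, near 100% | 1.00 | 3.35 |
| 50% → 60% | 1.50 | 3.86 |
| 50% → 40% | 0.67 | 2.49 |

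For 50% in both: (0.075/0.925)/(0.025/0.975) = 3.16. For 50% to 40%: (0.060/0.940)/(0.025/0.975) = 2.49. Starting from 50%, the share would have to fall to 0.025/0.15 = 16.7% before the all-student OR reached 1.

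**Precision of the referred-only model.** Each side of the main contrast has 70 × 50 = 3500 student records, of which 0.05 × 3500 = 175 and 0.15 × 3500 = 525 are expected to carry a referral. At a 50% share the variance of the log OR is 4·D0/175 + 4·D1/525, where D is the design effect.
- ICC 0 (D0 = D1 = 1): SE = 0.175; 95% interval around an OR of 1.0 is 0.71 to 1.41.
- ICC 0.124 assumed also for eligibility among referred students, with referral counts per class following a beta-binomial with the same ICC: the size-weighted number of referrals per class is mean + variance/mean. This is 2.5 + 0.95 × 7.076 = 9.22 and 7.5 + 0.85 × 7.076 = 13.51, where 7.076 = 1 + 49 × 0.124. Then D0 = 1 + 8.22 × 0.124 = 2.02 and D1 = 1 + 12.51 × 0.124 = 2.55. SE = √(4 × 2.02/175 + 4 × 2.55/525) = 0.256; interval 0.61 to 1.65.

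The second calculation ignores covariance between periods of the same class.

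**The case against.** The case that the plan already means referred students is strong.
- The equation completes a sentence about a referred adolescent, so its 0 can be read as 'referred but not eligible'.
- Section 6.4 also says that Y is as before while cutting the data to period 2, so the phrase seems to carry notation rather than a record set.
- Items 3 and 4 of 6.3 also take their model from 6.2, yet apply it to students who were referred and have SDQ scores. There the reference can only mean model form.
- Section 4.2 collects these data from referred students only, so zeros for everyone else would be an added step.

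All of this stands, and it makes the all-student model the less likely reading. It does not remove the problem. The target sentence names a different quantity from Table 1, and the lead-in does not define the analysis set. Items 3 and 4 state their restriction to referred students in plain words, whereas item 1 follows its lead-in with a referral back to 6.2.

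A reader might go further and infer that the SAP commits to the all-student model, or that odds ratios near 3 are what the trial will report. The documents do not support either. A reader might also extend the point to self-referral. That equation too gives 0 to every other case, and its hypothesis is not worded as conditional on referral. But Table 1 and the text just before the equation define 0 as referral by another source, and Y is not carried over from 6.2 there. For self-referral it is a matter of wording only.

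**Conclusion.** The eligibility item is inconsistently worded, and the inconsistency leaves the quantity to be estimated open for a secondary outcome. Most of the SAP supports a model among referred students; the target sentence, the coding of 0 and the link to 6.2 together permit a model over all enrolled students.

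The consequence is conditional on that second reading being followed. At referral rates of 5% and 15%, any equal eligible share would give an OR of 3.00 to 3.35 instead of 1.00, and a fall from 50% to 40% would change the apparent direction (2.49 instead of 0.67). The shares are assumptions. None of this arises if the model is restricted to referred students. The point should be settled before analysis, because the correction is small and the possible misreading is of a stated hypothesis.

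**What to change.** In 6.3, item 1:
- State that the eligibility model is fitted only to student-period records with a referral in that period.
- Define the outcome as 1 = eligible; 0 = referred and assessed but not eligible; missing = referred but not assessed. Count the missing by condition, in line with the complete-case rule in 6.5 and the reporting of post-referral losses in 5.2.
- Delete the statement that Y carries over from 6.2, and keep the reference to 6.2 for the model form only.
- Reword the target sentence so that it names eligibility among referred adolescents.

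For consistency, write the 0 in the self-referral equation as referral by another source. If yield of eligible referrals per enrolled student is also of interest, list it as a separately named outcome.

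The cost is SAP wording, plus acceptance of the precision that the Table 1 outcome carries: about 175 and 525 referred records for the main contrast, fewer once unassessed students are set to missing. At a 50% share this gives a 95% interval around an OR of 1.0 of about 0.71 to 1.41 with ICC 0, or about 0.61 to 1.65 under the ICC and beta-binomial assumptions above. Classes without a referral in a period contribute nothing to that period: at a 5% referral rate, about 8% of classes if students are independent (0.95^50 = 0.077), or about 46% under the beta-binomial with ICC 0.124.

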6.4 Sensitivity analysis

The sensitivity analyses is based on the methods described in Thompson et al, 2018 (10) which is also used for calculating the power of the study. It uses data from the 2nd period only, since it is in this period where the two conditions differ most transparently: sensitization intervention versus no sensitization intervention. We will use GEE method to arrive at population averaged estimates of the effects of exposure to the interventions across the control and intervention conditions. As the power calculation for this trial is based on this method, we will assess the robustness of the results obtained by the primary method of analysis using this method.

To estimate the intervention effect, we need to estimate the parameters in the following regression equation

$$logit(P(Y_{ijkl})) = \mu + \theta X_i$$

where Y_{ijkl} is as before, μ is a constant, θ is the parameter of interest (the population-averaged estimate of the effect of the intervention), X_i is in indicator variable ($X_i = 0$ for the control condition and $X_i = 1$ for the intervention condition).

A separate file with a sub-set of data with all observations pertaining to time period 2 will be created for the analysis. Having data with one record for each student, and a variable to indicate the class in which the observations are nested (class_id), an indicator for being assigned to the intervention condition (intervention) and an indicator for the outcome variable of being referred (referred), the following stata commands will be used to analyse the intervention effect in period 2. We will first specify the panel data structure with clustering of data at class level using the command "xtset" and then specify the GEE model through the stata command "xtgee".

"xtset class_id"

STATISTICAL ANALYSIS PLAN FOR THE SENSITIZATION TRIAL

"xtgee referred intervention, family(binomial) link(logit) corr(independent) vce(robust)"

6.5 Statistical considerations

95% confidence intervals and p-values will be calculated for all outcomes.

Intention to treat analysis: All the classes randomised to receive the classroom sensitization intervention throughout the trial will be included in the analysis and will be considered to be in the respective condition to which they were assigned initially, irrespective of the receipt of the intervention.

Missing data: The number (%) of participants with complete data will be reported. The primary analyses will be complete cases, with adjustments made for baseline variables which are associated with the outcome and/or missingness, to account for missing data.

No interim analysis of outcomes will be undertaken.

6.6 Other analysis

The intracluster correlation coefficient will be calculated and its impact on the assumed power of the trial will be assessed post-hoc.

7. Ethical considerations

Ethical approval has been obtained from the ethics committees of Sangath, Goa (Ref:RP_2018_47), and Harvard Medical School (Ref:MOD17-0379-03). The trial is registered prospectively on ClinicalTrials.gov and identified through protocol number NCT03633916 (available at: https://clinicaltrials.gov/ct2/show/NCT03633916).

References

1. Parikh R, Michelson D, Malik K, Shinde S, Weiss HA, Hoogendoorn A, et al. The effectiveness of a low-intensity problem-solving intervention for common adolescent mental health problems in New Delhi, India: protocol for a school-based, individually randomized controlled treatment trial with an embedded stepped-wedge cluster randomized controlled recruitment trial. Trials. submitted.

Appendix 1: Stratified randomisation for the cluster randomised controlled trial

The following steps were undertaken to identify 1) the 70 classes to be included in this trial, and 2) random allocation of these 70 classes into two sequences that will receive the classroom sensitisation (intervention condition) across the two steps (figure 1).

1. List the population of classes for sensitization trail

The population of classes includes all classes in the 6 schools from 9th-12th grades = 172 classes. The schools are of a variable size with differing numbers of classes across grades 9-12. 54 classes had received classroom sensitisation in earlier pilot work, reducing the available classes for the trial to 118 (Tables 1.1a and 1.1b).

Table 1.1a: Total number of classes and available classes (not exposed to sensitization till date) in each of the participating schools

Schools	9 th	10th	11 th	12th	Total
GBSSS Mahipalpur = 1* (total classes)	11	11	5	3	30
Classes available for TRIAL	6	10	5	0**	21
GBSSS, Molarband = 2* (total classes)	10	5	5	6	26
Classes available for TRIAL	5	5	5	6	21
SBV, Molarband = 3* (total classes)	8	8	5	5	26
Classes available for TRIAL	8	7	3	5	23
GGSSS Molarband = 4* (total classes)	14	7	5	5	31
Classes available for TRIAL	9	7	5	0**	21
ASMS-SKV, Mahipalpur = 5* (total classes)	14	8	6	6	34
Classes available for TRIAL	0*	7	4	6	17
SBV Co-Ed, Vasant Vihar = 6* (total classes)	12	4	4	5	25
Classes available for TRIAL	6	0**	4	5	15
Total number of classes (across the 6 schools)	69	43	30	30	172
Classes available for TRIAL	34	36	26	22	118

Notes: *Unique numerical code assigned to each of the participating schools

**Inadvertently all classes from some grades in some schools were used in pilot activities, where no classes are available for the trial

Table 1.1b: List of all the available classes (n=118) for the sensitization trial

	School no. 1	School no. 2	School no 3	School no 4	School no 5	School no 6
9 th grade	1-9-E	2-9-A	3-9-A	4-9-A		6-9-B
	1-9-F	2-9-B	3-9-B	4-9-B		6-9-D
	1-9-G	2-9-G	3-9-C	4-9-C		6-9-E

	School no. 1	School no. 2	School no 3	School no 4	School no 5	School no 6
	1-9-H	2-9-J	3-9-D	4-9-D		6-9-F
	1-9-I	2-9-К	3-9-Е	4-9-F		6-9-J
	1-9-К		3-9-F	4-9-G		6-9-K
			3-9-G	4-9-J		
			3-9-H	4-9-К		
				4-9-L		
10 th grade	1-10-В	2-10-A	3-10-A	4-10-A	5-10-A	
	1-10-C	2-10-В	3-10-В	4-10-B	5-10-C	
	1-10-D	2-10-C	3-10-C	4-10-C	5-10-D	
	1-10-E	2-10-D	3-10-D	4-10-D	5-10-E	
	1-10-F	2-10-Е	3-10-Е	4-10-E	5-10-F	
	1-10-G		3-10-F	4-10-F	5-10-G	
	1-10-H		3-10-H	4-10-G	5-10-H	
	1-10-I					
	1-10-J					
	1-10-K					
11 th grade	1-11-A	2-11-A	3-11-A	4-11-A	5-11-A	6-11-A
	1-11-B	2-11-B	3-11-B	4-11-B	5-11-D	6-11-B
	1-11-C	2-11-C	3-11-D	4-11-C	5-11-E	6-11-C
	1-11-D	2-11-D		4-11-D	5-11-F	6-11-D
	1-11-E	2-11-E		4-11-E		
12 th grade		2-12-A	3-12-A		5-12-A	6-12-A
		2-12-B	3-12-B		5-12-B	6-12-B
		2-12-C	3-12-C		5-12-C	6-12-C
		2-12-D	3-12-D		5-12-D	6-12-D
		2-12-Е	3-12-Е		5-12-E	6-12-E
		2-12-F			5-12-F	

Notes: All classes are uniquely identified here using "school number-grade-section" format

2. Decide number of classes from each grade and school:

The numbers of classes from each grade to be selected (n) were calculated using the formula for proportional allocation (Table 1.2a):

n = total number of classes in the strata * (N/T)

where, n= sub-sample of a classes from a specific grade to be selected; N = total sample size = 70; T = Total number of classes = 172

When the classes were not available in a specific grade/school, these were balanced with other grades in the same school to achieve the total number of classes required per school. This was then balanced with classes from within the same grade across other schools to ensure that the numbers to be selected for each grade were also maintained (Table 1.2b)

Schools	9th	10th	11 th	12 th	Sample to be selected
GBSSS Mahipalpur = 1					12
GBSSS, Molarband =2					11
SBV, Molarband = 3					11
GGSSS Molarband 4					13
ASMS-SKV, Mahipalpur = 5					13
SBV Co-Ed, Vasant Vihar = 6					10
Numbers to select for the trial	28	18	12	12	70

Table 1.2a: Number of classes to be selected for sensitization trial from each school

Table 1.2b: Sample to be selected from each school and for each grade

Schools	9 th	10th	11 th	12 th	Sample to be selected
GBSSS Mahipalpur = 1	6	4	2	0*	12
GBSSS, Molarband =2	5	2	2	2	11
SBV, Molarband = 3	4	2	2	3	11
GGSSS Molarband 4	7	4	2	0*	13
ASMS-SKV, Mahipalpur = 5	0*	6	2	5	13
SBV Co-Ed, Vasant Vihar = 6	6	0*	2	2	10
Numbers to select for the trial	28	18	12	12	70

3. Select the sample of 70 classes through stratified randomisation

Stratification is planned at two levels – first school and then grade to account for unknown school level factors that may influence the referral (e.g., general support or lack thereof to school counselling service, and researcher/counsellor related factors) and factors associated with grades (e.g. younger students in grade 9th compared to 12th, and inherent academic pressure in specific grades, such as those with board exams).

70 classes as per the sub-samples drawn in table 1.2b were then selected from the 118 available classes using steps as follows:

- First, the entire list of classes was entered on excel. Each class was identified by a unique id (school code grade division).
- Then random numbers were allocated to each class by using the rand() command.
- After the random numbers were generated they were pasted as values on the same cells so that the numbers will not change subsequently.
- Then the list was sorted by school, grade and value of random number (smallest to largest) in that order using the "custom sort" dialog box.
- Using the smallest value of random number as a guide, the required numbers of classes were selected within each school and standard.

- The complete list of 70 classes arrived after this process is included in Table 1.3. The selected classes are highlighted in yellow and is used for further process of creating blocks and randomisation.
- It was decided that in the rare instance that a selected class was dissolved or merged with another class – which was anticipated as the admission process was incomplete when the randomisation was undertaken – the next class in the random list will be included to replace the unavailable class.

Table 1.3: List of n=118 classes and selection of n=70 classes (yellow) for the sensitization trial using random numbers generated in excel

		Class	Random number
School	Standard	(school no. – standard –	(using function
number	(9 th /10 th /11 th /12 th)	division)	=rand())
1	9	1-9-H	0.192594
1	9	1-9-E	0.430515
1	9	1-9-G	0.541229
1	9	1-9-F	0.663142
1	9	1-9-I	0.704873
1	9	1-9-К	0.752422
1	10	1-10-G (class dissolved)	0.147472
1	10	1-10-F	0.15537
1	10	1-10-C	0.208894
1	10	1-10-K (class dissolved)	0.340698
1	10	1-10-I (class is dissolved)	0.359488
1	10	1-10-E	0.419727
1	10	1-10-H (class dissolved)	0.482554
1	10	1-10-J (class dissolved)	0.626517
1	10	1-10-B (class dissolved)	0.681298
1	10	1-10-D	0.770563
1	11	1-11-E	0.061504
1	11	1-11-A	0.379209
1	11	1-11-C	0.595781
1	11	1-11-D	0.714406
1	11	1-11-B	0.854851
2	9	2-9-J	0.184087
2	9	2-9-G	0.284391
2	9	2-9-A	0.462558
2	9	2-9-K (class dissolved)	0.503076
2	9	2-9-В	0.717554
2	10	2-10-В	0.012059
2	10	2-10-Е	0.060256

		Class	Random number
School	Standard	(school no. – standard –	(using function
number	(9 th /10 th /11 th /12 th)	division)	=rand())
2	10	2-10-C	0.09483
2	10	2-10-A	0.315278
2	10	2-10-D	0.338341
2	11	2-11-A	0.076932
2	11	2-11-D	0.151911
2	11	2-11-В	0.382449
2	11	2-11-C	0.793082
2	11	2-11-E	0.799644
2	12	2-12-D	0.347844
2	12	2-12-C	0.412709
2	12	2-12-F	0.440067
2	12	2-12-В	0.509551
2	12	2-12-E	0.588307
2	12	2-12-A	0.974578
3	9	3-9-G	0.084368
3	9	3-9-Е	0.220811
3	9	3-9-Н	0.29292
3	9	3-9-A	0.295531
3	9	3-9-В	0.483728
3	9	3-9-C	0.518274
3	9	3-9-F	0.75435
3	9	3-9-D	0.966725
3	10	3-10-C	0.146656
3	10	3-10-Е	0.179899
3	10	3-10-D	0.481394
3	10	3-10-Н	0.499846
3	10	3-10-F	0.505348
3	10	3-10-A	0.739538
3	10	3-10-В	0.954587
3	11	3-11-A	0.129143
3	11	3-11-В	0.452066
3	11	3-11-D	0.580499
3	12	3-12-D	0.089252
3	12	3-12-Е	0.178107
3	12	3-12-A	0.369123
3	12	3-12-В	0.39269
3	12	3-12-C	0.879363
4	9	4-9-K	0.02463
4	9	4-9-B	0.058254

		Class	Random number
School	Standard	(school no. – standard –	(using function
number	(9 th /10 th /11 th /12 th)	division)	=rand())
4	9	4-9-G	0.282987
4	9	4-9-L	0.425811
4	9	4-9-F	0.544048
4	9	4-9-J	0.741914
4	9	4-9-A	0.877333
4	9	4-9-D	0.896587
4	9	4-9-C	0.988156
4	10	4-10-G	0.184097
4	10	4-10-C	0.361362
4	10	4-10-D	0.434305
4	10	4-10-F	0.722952
4	10	4-10-A	0.779491
4	10	4-10-E	0.83026
4	10	4-10-В	0.862193
4	11	4-11-B	0.123751
4	11	4-11-A	0.370797
4	11	4-11-D	0.767838
4	11	4-11-E	0.856566
4	11	4-11-C	0.867977
5	10	5-10-F	0.286355
5	10	5-10-Е	0.393016
5	10	5-10-A	0.460435
5	10	5-10-C	0.488292
5	10	5-10-G	0.596692
5	10	5-10-Н	0.760017
5	10	5-10-D	0.858051
5	11	5-11-A	0.194647
5	11	5-11-F	0.503224
5	11	5-11-E	0.570214
5	11	5-11-D	0.628346
5	12	5-12-D	0.213647
5	12	5-12-A	0.335742
5	12	5-12-C	0.478392
5	12	5-12-E	0.549698
5	12	5-12-B	0.795617
5	12	5-12-F	0.966802
6	9	6-9-K (class dissolved)	0.142101
6	9	6-9-F	0.152092
6	9	6-9-E	0.250829

		Class	Random number
School	Standard	(school no. – standard –	(using function
number	(9 th /10 th /11 th /12 th)	division)	=rand())
6	9	6-9-В	0.935468
6	9	6-9-J	0.939516
6	9	6-9-D	0.966047
6	11	6-11-A	0.192713
6	11	6-11-B	0.201508
6	11	6-11-C	0.666467
6	11	6-11-D	0.987525
6	12	6-12-C	0.027382
6	12	6-12-Е	0.255308
6	12	6-12-A	0.585509
6	12	6-12-D	0.713415
6	12	6-12-В	0.895144

4. Creating blocks and randomisation

- Blocks: As the selected numbers of classes within each school-grade combination is often small, block size of 2 was used to assign the classes to one of the two groups, so that allocation of classes can be balanced across both the treatment groups.
- Creating blocks: 2 classes within the same school and standard were grouped together to form a block. If this was not possible, then classes were clubbed together within the classes from same grade from other schools to form blocks of two.
- Each of the blocks thus created were numbered sequentially from 1-35.
- Randomisation is required to allocate the classes across two sequences:
 - Sequence 1 Group A: 1-35 classes to receive the intervention condition in the second time period.
 - Sequence 2 Group B: 36-70 classes to receive the intervention condition in the third time period.
- The first 17 blocks were labelled AB and subsequent 18 blocks were labelled BA. Using excel command rand() a random number was allocated to each of these blocks. With sorting on random number, AB and BA were randomly allocated to each of the 35 blocks (Table 1.4).
- These classes within each block was then assigned to the treatment group as per the sequence generated in table 1.4. The final list of classes randomised in two groups as per the above process is re-produced in table 1.5, and will be used for the trial.

Table 1.4: Rando	m allocation	of the blocks
------------------	--------------	---------------

Block number for		
randomisation	Blocks	Random number
1	AB	0.997221
2	BA	0.804859
3	AB	0.814548
4	AB	0.773763
5	AB	0.152418
6	BA	0.007255
7	BA	0.356458
8	BA	0.654178
9	AB	0.817778
10	BA	0.212944
11	AB	0.115815
12	AB	0.22788
13	AB	0.673958
14	BA	0.031788
15	AB	0.00872
16	BA	0.298582
17	BA	0.282199
18	AB	0.43279
19	BA	0.716775
20	AB	0.874177
21	AB	0.262606
22	BA	0.936284
23	BA	0.805721
24	BA	0.319226
25	BA	0.24751
26	AB	0.953943
27	BA	0.809131
28	BA	0.609128
29	BA	0.485599
30	BA	0.924817
31	BA	0.28247
32	AB	0.7649
33	AB	0.171817
34	AB	0.636414
35	AB	0.042925

Sequence 1: Group A (Classes 1-35)		5)	Sequence 2: Group B (Classes 36-70)		
School code	Grade	Class	School code	Grade	Class
1	9	1-9-E	1	9	1-9-F
1	9	1-9-H	1	9	1-9-G
1	9	1-9-I	1	9	1-9-К
1	10	1-10-C	1	10	1-10-F
1	10	1-10-E *	1	10	1-10-D *
1	11	1-11-E	1	11	1-11-A
2	9	2-9-B	2	9	2-9-A
2	9	2-9-J	2	9	2-9-G
2	9	2-10-C *	2	10	2-10-В
2	10	2-10-Е	2	11	2-11-D
2	11	2-11-A	2	12	2-12-D
2	12	2-12-C	3	9	3-9-E
3	9	3-9-A	3	9	3-9-G
3	9	3-9-H	3	10	3-10-Е
3	10	3-10-C	3	11	3-11-A
3	11	3-11-B	3	12	3-12-A
3	12	3-12-D	4	9	4-9-A
3	12	3-12-Е	4	9	4-9-B
4	9	4-9-F	4	9	4-9-J
4	9	4-9-G	4	9	4-9-L
4	9	4-9-K	4	10	4-10-C
4	10	4-10-D	4	10	4-10-F
4	10	4-10-G	4	11	4-11-A
4	11	4-11-B	5	10	5-10-A
5	10	5-10-C	5	10	5-10-F
5	10	5-10-E	5	10	5-10-G
5	10	5-10-H	5	11	5-11-A
5	11	5-11-F	5	12	5-12-A
5	12	5-12-C	5	12	5-12-B
5	12	5-12-E	5	12	5-12-D
6	9	6-9-D	6	9	6-9-B
6	9	6-9-E	6	9	6-12-D *
6	9	6-9-J	6	9	6-12-A *
6	11	6-11-A	6	11	6-11-B
6	12	6-12-C	6	12	6-12-E

Table 1.5: Allocation of 70 classes equally across sequence 1 (Group A) and sequence 2 (Group B)

Notes: *classes were added as replacements for the classes that were dissolved before the commencement of the trial.
